Negative Pressure Wound
Therapy for Prevention of
Wound Infection after Heart
Surgery

NCT# 02020018

September 23, 2016

IRB Protocol Template

Title: Negative pressure wound therapy for prevention of wound infection after heart surgery

Protocol Version/Date: September 23, 2016

IRB#: 16-007901 (Original 13-001832)

PI: [name] M.D.

Abstract:

Wound-related complications after median sternotomy are important problems associated with increased morbidity and mortality, and lead to increase costs secondary to increase length of hospital stay and the need for repeated surgical procedures in these patients. Risk factors include: chronic obstructive pulmonary disease (COPD), smoking, diabetes, bilateral harvest of the internal thoracic artery, and, in particular, obesity have been identified as major risk factors. Breakdown of skin sutures facilitates entry of bacteria into the deeper layers and presents the initial step in the development of the majority of wound infections after median sternotomy. This theory may explain why the risk of wound infection is particularly high in obese patients, because the shear and traction forces on skin sutures are high. Negative pressure wound therapy have been used in different specialities to treat infected or open wounds, and has been proven to be of great benefit in multiple studies. Its use as a primary prevention has not been the routine after cardiac surgery in high risk patients. We hypothesize that negative pressure wound dressing application on clean skin immediately after suturing in the operating room for 6-7 days will prevent skin breakdown in the early periods after surgery and will decrease the incidence of wound related complications and infection. This may lead to a change in practice when dealing with high risk individuals. The purpose of this study was to compare a new commercially available negative pressure wound therapy (NPWT) system (Prevena Incision Management System; KCI, San Antonio, Tex) and conventional sterile dry wound dressing in a high-risk group (ie, obese patients), with special regard to wound complications and infections. Of note the "Prevena incision management system" is an FDA-approved device with 510K clearance.

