Schematic Design of the Study: There will be two groups: the first will include "Prospective non-randomized" part which will include patients who agreed to participate and have wound VAC applied to their incision postoperatively for 6-7 days (this information was collected under IRB 13-001832). The second group will include "retrospective chart review" for standard wound care after heart surgery with no wound VAC.

Aims:

Comparing the outcome of negative pressure wound therapy and conventional sterile dressing for high risk patients undergoing open heart surgery through median sternotomy

Methods

Description of Recruitment Methods:

How will subjects be identified?

Chart review and cardiac surgery database

How will subjects be contacted?

Follow-up routine postoperative visits and chart reviews

Recruitment Materials (if applicable):

Chart review

Subject Population:

Number: 950

The prospective portion will include 300 patients in whom the Prevena wound VAC system will be applied and the retrospective portion will include the remaining 650 patients.

Gender:

Male 450

Female 500
Ages: 18 to 100 years

Inclusion Criteria:

- BMI>30
- Severe COPD
- Steroid-dependent
- Type-I diabetes (insulin-dependent)
- Heart and lung transplant patients
- Preoperative tracheostomy
- Undergoing median sternotomy for open heart surgery between 2013-2014

Exclusion Criteria:

- Thoracotomy
- Type-II diabetes
- BMI<30

Step-by-Step Schedule (include all procedures, therapies – attach a table or flow chart if there are multiple procedures or visits and indicate the window of number of days in which the participant may return for follow-up visits):

N/A

Biospecimen (types, number, volume, processing, storage):

N/A

Plan for Dose Modification if Toxicity occurs (if applicable):

N/A

Statistical Considerations

Endpoints

Primary: wound infection
Secondary: wound breakdown
Length of stay
Re-operation
Mortality due to mediastinitis

Protocol form, page 2

Human Safety Aspects

Risks: Minimal risk study

Individual Subject Stopping Rules (if applicable):

DSMB (if applicable):

Members:

Charter:

Stopping Rules for Efficacy and Safety (if applicable):

Questionnaires that ask about Depression (if applicable)

Included in study? Yes No If "Yes", state the plan of management for subjects with possible depression:

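### Does leaving the wound site out of the primary endpoint dilute the comparison and forfeit a check for bias?

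*Combined protocol and SAP*

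**What the plan says.** Under Statistical Considerations, Endpoints, the two wound outcomes are "Primary: wound infection" and "Secondary: wound breakdown". Neither names an anatomical site. The title is just as general, and so is the hypothesis in the Abstract, that the dressing "will decrease the incidence of wound related complications and infection".

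The surrounding text is more specific. The Abstract opens with "Wound-related complications after median sternotomy are important problems". The Aims concern "high risk patients undergoing open heart surgery through median sternotomy". The Schematic Design says that device patients "have wound VAC applied to their incision postoperatively for 6-7 days", with incision in the singular. Median sternotomy is an inclusion criterion, thoracotomy is an exclusion, and the last secondary endpoint is "Mortality due to mediastinitis".

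The device group is a prospective, non-randomised set of 300 consenting patients. The 650 controls come from retrospective chart review. The protocol plans no outcome that should be unaffected by the dressing.

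**The concern.** The device acts on one wound, while the outcome as written could include any wound. Heart-surgery patients may have others, and the protocol itself admits patients with a preoperative tracheostomy. If infections away from the sternum occur equally often in both groups and are counted, the relative risk moves toward 1 and power falls.

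The groups also differ in how patients enter and how data are captured. An infection that the dressing cannot prevent should then show no difference between groups, and a difference would warn of case-mix or detection bias. Folding such infections into the primary count would forgo that warning. Both problems appear to be curable with a few words and one extra data field.

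**Working it through.** **What the documents give.** The group sizes are 300 and 650, total 950. They state no alpha, power, infection rate, effect size or other-site rate, so there is no design calculation to reproduce. Every rate below is an assumption.

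**Dilution.** Let p be the sternal rate and q the other-site rate, taken as independent and unaffected by the device. The observed rate is 1 − (1 − p)(1 − q). Power is for a two-sided 5% test of two proportions with pooled variance under the null: Φ[(|d| − 1.96·s0)/s1]. Here d is the difference in rates, s0 its standard error from the pooled rate and s1 its standard error from the separate rates.

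Worked case: p = 0.08 in controls, 0.04 with the device, q = 0.02 in both.
- Controls: 1 − 0.92 × 0.98 = 0.0984. Device: 1 − 0.96 × 0.98 = 0.0592.
- Relative risk: 0.0592/0.0984 = 0.60. Difference: 0.0392.
- s0 = 0.0196, s1 = 0.0180, so power = Φ[(0.0392 − 1.96 × 0.0196)/0.0180], about 52%.

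| Other-site rate, both groups | Control | Device | RR | Difference (points) | Power |
|---|---|---|---|---|---|
| 0% | 8.00% | 4.00% | 0.50 | 4.0 | 64% |
| 2% | 9.84% | 5.92% | 0.60 | 3.9 | 52% |
| 4% | 11.68% | 7.84% | 0.67 | 3.8 | 43% |
| 8% | 15.36% | 11.68% | 0.76 | 3.7 | 32% |

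With sternal rates of 5% and 2.5%, a 4% other-site rate takes the relative risk to 0.73 and power from 42% to 23%. With 15% and 7.5%, a 2% other-site rate takes power from 92% to 87%. If nothing outside the sternum is counted, nothing changes.

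**Direction.** Attenuation needs equal other-site rates. Keep the sternal rates at 8% and 4% and let the other-site rates differ:
- Device 1%, control 4%: (1 − 0.96 × 0.99)/(1 − 0.92 × 0.96) = 0.0496/0.1168 = 0.42, further from 1 than 0.50.
- Device 4%, control 2%: 0.0784/0.0984 = 0.80, nearer to 1.

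The dilution argument assumes equal rates, while the bias argument assumes that detection or case mix differs between groups. The two cannot both be used at full strength.

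**Negative control.** Same test, with the control rate at q and the device rate at q times the bias ratio:

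| Other-site rate | Power, bias 0.7 | Power, bias 1.4 |
|---|---|---|
| 2% | 8% | 13% |
| 4% | 13% | 21% |
| 8% | 25% | 37% |
| 10% | 31% | 44% |
| 20% | 61% | 77% |

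Over the 2% to 8% range used for the dilution, the check would usually miss a bias of this size. Only at about 20% does it become useful, and that would require pooling in other non-sternal infections, which is a different outcome. A rule that withholds attribution to the device whenever the control estimate leans the same way as the primary, with no threshold, would be met by chance about half the time when there is no bias.

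**The case for a change.** The best case for a change is that an abstractor needs a written rule, however clear the context. Device data were collected under an earlier IRB number and control data come from charts, so an unwritten rule could be applied differently in the two groups. A tracheostomy site is one non-sternal wound that the protocol itself places in the population. Even 1% other-site infection would take power from 64% to 58% in the 8% versus 4% case, and stating the site costs a few words.

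The arithmetic stands, and so does the observation that the endpoint lines name no site. The step from there to a defect does not. Drain, cannulation and leg or arm harvest wounds appear nowhere in the documents; the only harvest mentioned is of the internal thoracic artery, as a risk factor. Preoperative tracheostomy applies to an unstated share of patients. Nothing says that infections at such sites would be counted in a study whose stated problem, aim and eligibility all concern the sternotomy.

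A negative-control outcome can be sensible in a non-randomised comparison, but statisticians would disagree about its worth here. Its power is low, a null result would not rule out bias, and the protocol has no adjusted model in which to run it. Charts could still be classified by site later, so the option is not lost. For the device group, whose data were already collected, that could mean going back to 300 records if site was not noted.

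**Conclusion.** No change is called for. The missing site is a detail that analysts would fill sensibly, because the document as a whole describes the sternotomy wound. The harm is conditional: it needs other-site infections to be counted, and attenuation also needs them to be equally frequent in both groups. If both held, the effect at assumed sternal rates of 8% and 4% would run from RR 0.60 and 52% power (2% other-site) to RR 0.76 and 32% power (8% other-site), against 0.50 and 64% without them. The risk difference would fall by no more than 0.3 points. None of these rates comes from the documents, and under the sternal reading the loss is zero. The negative control is an optional, low-powered addition, and leaving it out is a fair choice. This conclusion covers wound site only; it does not address the diagnostic criteria, depth, data source or time window of the endpoint.
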